--	---

	
(MMRM). The MMRM model will contain terms for baseline Hb measurement as covariate, treatment arm, visit, visit by treatment arm, and randomization stratification factors (except screening Hb values (<math>\leq 8\text{g/dL}</math> vs. <math>>8\text{g/dL}</math>) as fixed effects.
 
Due to the large amount of visits included in the model, the unstructured covariance pattern model will be tested against the less parameterized heterogeneous Toeplitz structure using the likelihood ratio test for nested models. If the algorithm for unstructured covariance pattern does not converge or the likelihood ratio test is not statistically significant then heterogeneous Toeplitz structure will be used. If this second model does not converge either, then the (homogeneous) Toeplitz structure will be tried and finally compound symmetry as a covariance structure to achieve convergence.
 
This null hypothesis will be rejected if the two-sided 95% confidence interval (CI) for the difference of least square means from the mixed model lies entirely above <math>-0.75\text{ g/dL}</math>.
 
Ex-US Submission: The primary efficacy endpoint for Ex-US submission is defined as the proportion of subjects who achieve a Hb response at two consecutive visits during the first 24 weeks of treatment, without rescue therapy within 6 weeks prior to the Hb response.
 
 
• A Hb response is defined, using central laboratory values, as: <math>\text{Hb} \geq 11.0\text{ g/dL}</math> and a Hb increase from baseline by <math>\geq 1.0\text{ g/dL}</math> in subjects whose baseline Hb <math>> 8.0\text{ g/dL}</math>, or
 
• Increase in Hb <math>\geq 2.0\text{ g/dL}</math> in subjects whose baseline Hb <math>\leq 8.0\text{ g/dL}</math>.
 
 
Rescue therapy for roxadustat treated subjects is defined as ESA rescue or RBC transfusion, and rescue therapy for epoetin alfa treated subjects is defined as RBC transfusion.
 
The hypothesis to be tested for the primary efficacy analysis is:
 
<math>H_0: \text{Hb response rate for subjects in the roxadustat arm} - \text{Hb response rate for subjects in the epoetin alfa arm} \leq -15\%</math>.
 
Versus
 
<math>H_1: \text{Hb response rate for subjects in the roxadustat arm} - \text{Hb response rate for subjects in the epoetin alfa arm} > -15\%</math>.
 
A two-sided 95% CI for the difference of 2 responder rates (roxadustat minus epoetin alfa) based on the Miettinen and Nurminen approach adjusting for treatment and other stratification factors will be calculated and the null hypothesis will be rejected if the lower bound of the 95% CI is greater than <math>-15\%</math>.
 
Safety:

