#### 8.4.3.1 Primary Efficacy Analysis

**US (FDA) Submission:** The primary efficacy endpoint for US (FDA) submission is defined as the mean Hb change from baseline to the average level during the Evaluation Period, defined as Week 28 until Week 52. The analysis will be based on the ITT population. Hb values under the influence of rescue therapy will not be censored for the primary efficacy analysis.

The primary hypothesis to be tested for the primary efficacy analysis is:

$H_0: Hb \text{ mean change from baseline to the average level from Week 28 to Week 52 in the roxadustat arm} \leq Hb \text{ mean change from baseline in the epoetin alfa arm minus } 0.75 \text{ g/dL}$

*Versus:*

$H_1: Hb \text{ change from baseline to the average level of Week 28 to Week 52 in the roxadustat arm} > Hb \text{ mean change from baseline in the epoetin alfa arm minus } 0.75 \text{ g/dL}$

A Multiple Imputation Analysis of Covariance (MI ANCOVA) model will be used for the primary endpoint (change from baseline in Hb from Week 28 to Week 52).

The model will contain terms for treatment arm, baseline Hb measurement, and randomization stratification factors, except for Screening Hb values ( $\leq 8\text{g/dL}$  vs.  $> 8\text{g/dL}$ ). Detailed analysis of the primary [efficacy] endpoint will be outlined in the SAP. The primary efficacy analysis for US [FDA] and sensitivity analysis for the first secondary endpoint for ex-US submissions will be based on the estimated difference between the two treatment arms of the overall mean effects throughout the evaluation period based on the MI ANCOVA model.

In addition, as a sensitivity analysis, the primary efficacy endpoint for US [FDA] and primary analysis for the first secondary endpoint for ex-US submissions will be analyzed using the analysis of a model for repeat measures (MMRM). The MMRM model will contain terms for baseline Hb, as covariate, treatment arm, visit, visits by treatment arm, and randomization stratification factors (except for Screening Hb values ( $\leq 8\text{g/dL}$  vs  $> 8\text{g/dL}$ ) as fixed effects. Additional analysis using pattern mixture approaches would be detailed in the SAP.

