Due to the large amount of visits to include in the model, the unstructured covariance pattern model will be tested against the less parameterized heterogeneous Toeplitz structure using the likelihood ratio test for nested models. If the algorithm for unstructured covariance pattern does not converge or the likelihood ratio test is not statistically significant then heterogeneous Toeplitz structure will be used. If this second model does not converge either, then the (homogeneous) Toeplitz structure will be tried and finally compound symmetry as a covariance structure to achieve convergence.

This null hypothesis will be rejected if the two-sided 95% CI for the difference (roxadustat minus epoetin alfa) of two least square means from the mixed model lies entirely above  $-0.75 \text{ g/dL}$ .

Hb values under the influence of a rescue therapy will not be censored in the primary analysis.

**Ex-US Submission:** The primary efficacy endpoint for Ex-US submission is defined as the proportion of subjects who achieve a Hb response at two consecutive visits during the first 24 weeks of treatment, without rescue therapy within 6 weeks prior to the Hb response.

- A Hb response is defined, using central laboratory values, as:  $Hb \geq 11.0 \text{ g/dL}$  and a Hb increase from baseline by  $\geq 1.0 \text{ g/dL}$  in subjects whose baseline  $Hb > 8.0 \text{ g/dL}$ , or
- Increase in  $Hb \geq 2.0 \text{ g/dL}$  in subjects whose baseline  $Hb \leq 8.0 \text{ g/dL}$

Rescue therapy for roxadustat treated subjects is defined as ESA rescue or RBC transfusion, and rescue therapy for epoetin alfa treated subjects is defined as RBC transfusion.

The hypothesis to be tested for the primary efficacy analysis is:

$H_0: Hb \text{ response rate for subjects in the roxadustat arm} - Hb \text{ response rate for subjects in the epoetin alfa arm} \leq -15\%$

*Versus*

$H_1: Hb \text{ response rate for subjects in the roxadustat arm} - Hb \text{ response rate for subjects in the epoetin alfa arm} > -15\%$

A two-sided 95% CI for the difference of 2 responder rates (roxadustat minus epoetin alfa) based on the Miettinen & Nurminen approach adjusting for treatment and other stratification factors will be calculated and this null hypothesis will be rejected if the lower bound of the 95% CI is greater than -15%.

The stratification factors to be used in efficacy analyses are:

1. Geographical region
2. Screening Hb values ( $\leq 8 \text{ g/dL}$  vs.  $> 8 \text{ g/dL}$ )

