11.1.2 Primary Analysis

Efficacy analysis for superiority will be conducted on the ITT population for US (FDA) submission and on the FAS population for Ex-US submission.

Efficacy analysis for non-inferiority will be conducted on the ITT population for US (FDA) submission and on the PPS population for Ex-US submission.

US (FDA) Submission: The primary efficacy endpoint for US (FDA) submission is defined as the mean Hb change from baseline to the average level during the Evaluation Period, defined as Week 28 until Week 52. The analysis will be based on the ITT

population. Hb values under the influence of rescue therapy will not be censored for the primary efficacy analysis.

The primary hypothesis to be tested for the primary efficacy analysis is:

H_0 : Hb mean change from baseline to the average level from Week 28 to Week 52 in the roxadustat arm \leq Hb mean change from baseline in the epoetin alfa arm minus 0.75 g/dL

Versus:

H_1 : Hb mean change from baseline to the average level of Week 28 to Week 52 in the roxadustat arm $>$ Hb mean change from baseline in the epoetin alfa arm minus 0.75 g/dL

A multiple imputation analysis of covariance (MI ANCOVA) model will be used. The model will contain terms for treatment group, baseline Hb measurement, and stratification factors except Screening Hb values (≤ 8 g/dL vs. > 8 g/dL). The primary efficacy analysis will be based on the estimated difference between the two treatments overall mean effects throughout the evaluation period based on the pooled ANCOVA model.

This null hypothesis will be rejected if the two-sided 95% CI for the difference between the two treatment groups using MI ANCOVA model lies entirely above -0.75 g/dL.

The following steps will be used to conduct the primary analysis of the primary endpoint:

1. Generate 200 datasets, using seed 162345 for the U.S., where only intermittent missing hemoglobin data will be imputed for each treatment relying on non-missing data from all subjects within each treatment group using the Monte Carlo Markov Chain (MCMC) imputation model baseline hemoglobin, and the available non missing hemoglobin for each scheduled Week by treatment group.

The MCMC statement in the SAS PROC MI procedure with monotone option will be used. As a result, each dataset will only have missing ending data, or a monotone missing data pattern.

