2. For each dataset from step 1, missing ending data (hemoglobin up through end of evaluation period) will be imputed. As a result, 200 imputed complete datasets will be generated.

- Missing data at Week 1 will be imputed using the regression imputation model with baseline stratification factor, baseline and hemoglobin from Week 1, using the SAS PROC MI procedure with the REGRESSION option in the MONOTONE statement.
- The SAS PROC MI procedure will use data separately from each treatment subjects to impute the missing data for a specific Week (i.e. only those that need the imputation for the Week). Since subjects from the different treatment groups for that Week are excluded from the step, they will not contribute to the imputation for the Week.
- Repeat for all other scheduled Weeks sequentially (Week 2 to the end of evaluation period). Subjects whose missing data were imputed for previous Weeks will contribute to the imputation for the current Week.

- The regression imputation model includes an intercept and the slopes of the hemoglobin from previous Weeks.

3. Analyze each imputed complete dataset using the ANCOVA model using the mean of all observed or imputed Hb values within the evaluation period (Week 28 – 52). The model will contain terms for baseline Hb measurement as a covariate, treatment group and stratification factors except Screening Hb values (≤ 8 g/dL vs. > 8 g/dL) as fixed effects.

Sample SAS code:

```
PROC MIXED data=xx;
  class treatment categorical covariates;
  model change_Week36 = treatment covariates / solution;
  lsmeans treatment / diff cl;
  ods output Diffs=lsdiffs LSMeans=lsm solutionF=Parms;
  by _Imputation_;
run;
```

4. Combine estimates from the results for each of the 200 ANCOVA model using SAS PROC MIANALYZE.

```
PROC MIANALYZE parms(classvar=full)=lsdiffs;
  class treatment categorical covariates;
  modeleffects treatment;
  ods output ParameterEstimates=MIAN_lsdiffs;
run;
```

Report the results of the least-squares mean estimates of the change from baseline in hemoglobin during the evaluation period, the estimates of treatment effect (e.g. least-squares mean CFB in hemoglobin for the treatment group minus the least-squares mean CFB in hemoglobin for the active comparator group) and the corresponding p-values during the evaluation period.

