11.1.3.1 MMRM Model

A mixed model of repeated measures (MMRM) will be used as one sensitivity analysis for the primary endpoint for US Submission (change from baseline in Hb from Week 28 to Week 52).

The model will contain terms for treatment arm, baseline measurement, visit (up to Week 52), visit by treatment interaction, and stratification factors except Screening Hb values (≤ 8 g/dL vs. > 8 g/dL). The primary efficacy analysis (for US [FDA]) will be based on the estimated difference between the two treatments overall mean effects throughout the evaluation period based on the MMRM model. Hb values under the influence of a rescue therapy will not be censored in the primary analysis.

Due to the large amount of visits to include in the model, data up to Week 52, the unstructured covariance pattern model will be applied first. If the algorithm for unstructured covariance pattern does not converge or the likelihood ratio test is not statistically significant then heterogeneous Toeplitz structure will be used. If this second model does not converge either then the (homogeneous) Toeplitz structure will be tried and finally compound symmetry as a covariance structure to achieve convergence. If none of them converge, first order autoregressive (AR (1)) as a covariance structure will be used to achieve convergence.

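### The US primary rejection rule is worded on the mixed model in the protocol and on MI ANCOVA in the SAP, and one SAP sentence again calls the MMRM primary

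*Protocol*

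**What the plan says.** **Protocol, model.** Section 8.4.3.1 states: "A Multiple Imputation Analysis of Covariance (MI ANCOVA) model will be used for the primary endpoint". It bases the US primary efficacy analysis on the MI ANCOVA estimate and gives the MMRM the role of a sensitivity analysis for the US endpoint. The synopsis (Statistical Methods) assigns the same roles.

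**Protocol, rejection rule.** After the MMRM covariance-structure rules, 8.4.3.1 rejects the null if the two-sided 95% CI for the difference "of two least square means from the mixed model lies entirely above" −0.75 g/dL. The synopsis has the same rule in the same position: "for the difference of least square means from the mixed model lies entirely above" that margin.

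**SAP, rejection rule.** Section 11.1.2 rejects if the two-sided 95% CI "for the difference between the two treatment groups using MI ANCOVA model lies entirely above" −0.75 g/dL. Table 4 in 11.1.3 marks only the multiple-imputation ANCOVA row as primary and lists the MMRM as a separate row.

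**SAP, MMRM section.** Section 11.1.3.1 opens by calling the MMRM one sensitivity analysis for the US endpoint. It then says: "The primary efficacy analysis (for US [FDA]) will be based on the estimated difference between the two treatments overall mean effects" over the evaluation period, from the MMRM. The next sentence, on not censoring Hb values after rescue, also refers to the primary analysis.

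**SAP, sample code.** Step 3 of 11.1.2 defines the analysed value as the mean of all observed or imputed Hb values over Weeks 28–52. The sample code under that step reads "model change_Week36 = treatment covariates / solution".

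**The concern.** A non-inferiority decision needs one interval, from one model, for one response variable. Followed literally, the protocol's rejection rule decides the US primary hypothesis on the model that the preceding paragraph makes a sensitivity analysis. The SAP puts the decision on MI ANCOVA, but its MMRM section partly undoes that.

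This matters for three reasons:

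- The trial is open-label, and Protocol 8.4.5 itself links early finalisation of the SAP to avoiding bias.
- Rejecting this null opens the fixed-sequence testing of the secondary endpoints (Protocol 8.4.3.2, SAP 11.2).
- The two models treat missing visits differently. MI ANCOVA imputes within each arm, while the MMRM uses the available visits. Missing values in Weeks 28–52 are foreseeable, because treatment may last less than 52 weeks (Protocol 3.1).

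**Working it through.** **1. The places side by side**

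| Place | Model given the US primary role |
|---|---|
| Protocol synopsis, model description | MI ANCOVA (MMRM is sensitivity) |
| Protocol synopsis, rejection rule | mixed model |
| Protocol 8.4.3.1, model description | MI ANCOVA (MMRM is sensitivity) |
| Protocol 8.4.3.1, rejection rule | mixed model |
| SAP 11.1.2, rejection rule | MI ANCOVA |
| SAP 11.1.3, Table 4 | MI ANCOVA |
| SAP 11.1.3.1, opening sentence | MMRM is sensitivity |
| SAP 11.1.3.1, later sentence | MMRM |

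Only two models compete.

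**2. What the protocol means by the mixed model**

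A milder reading is an ANCOVA that happens to be fitted with PROC MIXED. Three things count against it:

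- Both rejection rules come straight after the MMRM covariance rules.
- Protocol 8.4.3.2 analyses the ex-US Week 28–36 endpoint by MMRM and then uses nearly the same rejection sentence, where the mixed model can only be the MMRM.
- In SAP 11.1.2 the MI ANCOVA interval comes from pooling 200 fits with PROC MIANALYZE, not from a single mixed model.

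**3. The plan's own design figure**

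The inconsistency has no figure of its own, but the design figure shows the scale. Inputs from SAP 5.1: difference −0.30 g/dL, margin −0.75 g/dL, SD 1.25 g/dL, at least 600 subjects. Allocation is 1:1, so 300 per arm.

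- SE = 1.25 × √(2/300) = 0.102 g/dL
- 95% CI half-width = 1.96 × 0.102 = 0.200 g/dL
- Power = Φ(0.45/0.102 − 1.96) = 99.28%

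This reproduces the stated power of at least 99%. Protocol 8.1 prints the assumed difference as 0.30 without a minus sign. The distance to the margin is then 1.05 g/dL and power exceeds 99.99%, so the statement holds either way.

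**4. MI ANCOVA against MMRM**

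The documents give no between-visit correlation and no dropout rate or pattern. The difference between the two estimates cannot be computed from them.

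**5. The sample code, if run literally**

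This is an illustration only. Assumptions not in the documents: compound symmetry with correlation ρ, and SD 1.25 g/dL applying to the mean of seven visits (Weeks 28, 32, 36, 40, 44, 48, 52, from the four-weekly schedule). Then

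SD at Week 36 = 1.25 / √[(1 + 6ρ)/7]

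For example, at ρ = 0.4: (1 + 2.4)/7 = 0.486, its square root is 0.697, and 1.25/0.697 = 1.79.

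| ρ | SD at Week 36 (g/dL) | Power, Week 36 only | Opposite decisions, true difference −0.30 |
|---|---|---|---|
| 0.4 | 1.79 | 86.7% | about 13% |
| 0.6 | 1.54 | 94.7% | about 5% |
| 0.8 | 1.37 | 98.0% | about 2% |

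The comparator is 99.3% power for the Week 28–52 mean. The last column is the simulated share of trials in which the two responses lead to different non-inferiority conclusions. The table sizes a coding mistake; it does not describe a planned analysis.

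**The case against.** The strongest reply is that the decision is already settled. Protocol 8.4.3.1 and 8.4.5 leave the detail to the SAP. SAP 11.1.2 states the only US primary rejection rule in that document, on MI ANCOVA, and specifies it down to the number of imputations, the seed and the pooling. Table 4 agrees. SAP 11.1.3.2.2 and 11.1.3.2.3 present the pattern-mixture models as checks on the ANCOVA results, and SAP 11.2.1.3 and 11.3.1.3 refer back to multiple imputation as the US primary method. The stray sentence in 11.1.3.1 sits under a sensitivity heading and carries no rejection rule. A later switch to the MMRM would openly contradict the SAP.

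Most of this stands. A reader might infer that the deciding interval is left unspecified; the SAP does not support that, since its rule is explicit. A reader might also infer from the code that a Week 36 analysis is a third route to the decision. It is not. The code is labelled as a sample and uses placeholder names, its own step defines the Week 28–52 mean, and no US hypothesis or rejection rule mentions Week 36.

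What the reply does not remove is that the protocol's rule, as printed, points to the sensitivity model, and that the SAP repeats the confusion once. Protocol 8.4.5 says significant changes to the analyses will be highlighted in the SAP; the SAP text available does not flag a changed rejection rule.

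**Conclusion.** Wrong as written, minor. The US primary rejection rule is inconsistently worded between MI ANCOVA and the MMRM, within the protocol and again within the SAP. The weight of the text favours MI ANCOVA. The Week 36 response in the sample code is a separate error inside the MI ANCOVA steps.

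The effect of choosing one model over the other is unquantified. It is probably small, because both models adjust for baseline Hb and average over the same evaluation period, but that is a judgement and not a result from the documents. The Week 36 figures depend wholly on the assumed correlation structure and apply only if the code were run as printed.

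**What to change.** 1. In the protocol synopsis and in 8.4.3.1, replace *the mixed model* with *the MI ANCOVA model* in the US rejection rule. Leave the similar sentence in 8.4.3.2, where the MMRM is intended for the ex-US Week 28–36 endpoint.
2. In SAP 11.1.3.1, relabel the sentence that calls the MMRM estimate the US primary efficacy analysis, and the primary-analysis wording in the sentence after it, as the MMRM sensitivity analysis.
3. In the SAP 11.1.2 sample code, replace `change_Week36` with a variable for the mean Week 28–52 change from baseline.

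The cost is wording only. Sample size, data collection and the planned set of analyses are unchanged.

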#### 8.4.3.2 Secondary Efficacy Analyses

Once the null hypothesis has been rejected for the primary endpoint (for both, US [FDA] and ex-US submissions), the secondary endpoints below will be tested using a fixed sequence testing procedure, in order to maintain the overall two-sided Type I error rate at 0.05. If p-value from a test is  $< 0.05$ , the claim of superiority (or noninferiority) will be considered met and the test will progress to the next comparison in sequence as follows:

- **US (FDA) Submission:** The first secondary endpoint for US (FDA) submission is defined as the proportion of subjects who achieve a Hb response at two consecutive visits during the first 24 weeks of treatment, without rescue therapy within 6 weeks prior to the Hb response.

A Hb response is defined, using central laboratory values, as:

- $Hb \geq 11.0 \text{ g/dL}$  and a Hb increase from baseline by  $\geq 1.0 \text{ g/dL}$  in subjects whose baseline  $Hb > 8.0 \text{ g/dL}$ , or
- Increase in  $Hb \geq 2.0 \text{ g/dL}$  in subjects whose baseline  $Hb \leq 8.0 \text{ g/dL}$

The hypothesis to be tested for this efficacy analysis is:

$H_0: Hb \text{ response rate for subjects in the roxadustat arm} - Hb \text{ response rate for subjects in the epoetin alfa arm} \leq 15\%$

*Versus*

$H_1: Hb \text{ response rate for subjects in the roxadustat arm} - Hb \text{ response rate for subjects in the epoetin alfa arm} > 15\%$

A two-sided 95% CI for the difference of 2 responder rates (roxadustat minus epoetin alfa) based on the Miettinen & Nurminen approach adjusting for treatment and other stratification factors will be calculated and  $H_0$  will be rejected if the lower bound of the 95% CI is greater than -15%.

- **Ex-US Submission:** The first secondary endpoint for Ex-US submission is the mean change in Hb levels from baseline to the average level during the Evaluation Period, defined as Week 28 until Week 36. This analysis will be based on the PPS population.

The primary hypothesis to be tested for this efficacy analysis is:

$H_0: Hb \text{ mean change from baseline to the average level from Week 28 to Week 36 in the roxadustat arm} \leq Hb \text{ mean change from baseline in the epoetin alfa arm minus } 0.75 \text{ g/dL}$

*Versus:*

$H_1: Hb \text{ change from baseline to the average level of Week 28 to Week 36 in the roxadustat group} > Hb \text{ mean change from baseline in the epoetin alfa group minus } 0.75 \text{ g/dL}$

This efficacy endpoint will be analyzed using a mixed model of repeated measures (MMRM) with Hb baseline value as covariate and treatment group and randomization stratification factors as fixed effects and MI ANCOVA as sensitivity analysis for Ex-US submission.

This null hypothesis will be rejected if the two-sided 95% CI for the difference of least square means from the mixed model is above -0.75 g/dL.

Hb values under the influence of a rescue therapy within 6 weeks prior to and during this 8-week evaluation period will be censored in the analysis.

- The average monthly iron use will be compared between the 2 treatment groups using an ANCOVA model with baseline iron replete as a covariate, and treatment group and randomization stratification factors as fixed effects. Superiority will be declared if the lower bound of the two-sided 95% CI of the difference between epoetin alfa and roxadustat exceeds zero.
- Mean change from baseline in LDL cholesterol averaged over Weeks 12 to 24 will be analyzed using an MMRM model with baseline LDL cholesterol as a covariate and treatment group, visit, visits by treatment arm, and randomization stratification factors as fixed effects. Superiority will be declared if the lower bound of the two-sided 95% CI of the difference between epoetin alfa and roxadustat exceeds zero.

- Proportion of subjects with exacerbation of hypertension, meeting at least 1 of the following criteria will be analyzed using CMH model adjusting for treatment group and stratification factors
  - Increase in blood pressure: An increase from baseline in systolic blood pressure (sBP) of  $\geq 20$  mm Hg and sBP  $> 170$  mmHg or an increase from baseline in diastolic blood pressure (dBP) of  $\geq 15$  mm Hg and dBP  $> 100$  mmHg. Increases from baseline in blood pressure must be confirmed by repeat measurement.

Noninferiority of roxadustat vs. epoetin alfa will be tested. Non-inferiority will be declared if the upper bound of the two-sided 95% CI of the hazard ratio is less than 1.3.

- Time to an increase in blood pressure (defined as an increase from baseline of  $\geq 20$  mm Hg systolic BP and sBP  $> 170$  mmHg or an increase from baseline of  $\geq 15$  mm Hg diastolic BP and dBP  $> 100$  mmHg). Time to an increase in blood pressure will be analyzed using the Cox Proportional Hazards model adjusting for treatment group and randomization stratification factors. Superiority of roxadustat vs. epoetin alfa will be tested.
- Mean change in mean arterial pressure (MAP) averaged over Weeks 8 to 12 will be analyzed using an MMRM model with baseline MAP as a covariate and treatment group, visit, visits by treatment arm, and randomization stratification factors as factors. Superiority will be declared if the lower bound of the two-sided 95% CI of the difference between epoetin alfa and roxadustat exceeds zero.

The time to achieve the first Hb response defined as the primary endpoint (for ex-US submission) will be analyzed using the Cox Proportional Hazards model adjusting for treatment group and other stratification factors. Non-inferiority of roxadustat vs. epoetin alfa will be tested. Non-inferiority will be declared if the upper bound of the two-sided 95% CI of the hazard ratio is less than 1.3.

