### 7.2 Secondary Endpoints

- **US (FDA) submission:** The proportion of subjects who achieve a Hb response at two consecutive visits during the first 24 weeks of treatment, without rescue therapy within 6 weeks prior to the Hb response.

A Hb response is defined, using central laboratory values, as

- Hb  $\geq 11.0$  g/dL and a Hb increase from baseline by  $\geq 1.0$  g/dL in subjects whose baseline Hb  $> 8.0$  g/dL, or
- Increase in Hb  $\geq 2.0$  g/dL in subjects whose baseline Hb  $\leq 8.0$  g/dL

- **Ex-US submission:** Mean Hb change from baseline to the average level during the Evaluation Period, defined as Week 28 until Week 36 without rescue therapy within 6 weeks prior to and during the evaluation period. This analysis will be based on the PPS population.

Both, US and ex-US Submissions:

- Average monthly IV iron use per subject during the Treatment Period. Mean change in low-density lipoprotein (LDL) cholesterol averaged over Weeks 12 to 24.

- Blood pressure effects:
  - Proportion of subjects with exacerbation of hypertension, meeting at least one of the following criteria:
    - Increase in BP: An increase from baseline of  $\geq 20$  mm Hg systolic BP and sBP  $>170$  mmHg, or an increase from baseline of  $\geq 15$  mm Hg diastolic BP and dBP $>100$  mmHg. Increases from baseline in blood pressure must be confirmed by repeat measurement.
  - Time to an increase in BP as defined above.
  - Mean change in mean arterial pressure (MAP) averaged over Weeks 8 to 12.
- Time to achieve first Hb response as defined by the primary endpoint (ex-US) (which is the secondary endpoint for the US [FDA]).

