### **8.4.5 Statistical Analysis Plan**

The Statistical Analysis Plan will provide details of the data analyses. As an open-label study the SAP will be finalized prior to accumulation of a substantial amount of data to ensure lack of bias. Any significant changes to the analyses described in this protocol will be highlighted in the SAP and the Clinical Study Report.

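### The protocol judges a CMH-analysed hypertension proportion by a hazard ratio, and the SAP's unflagged Cox replacement carries two margins and two diastolic thresholds

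*Protocol*

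**What the plan says.** **Protocol.** Section 7.2 defines a binary endpoint: "Proportion of subjects with exacerbation of hypertension, meeting at least" one blood-pressure criterion. Section 8.4.3.2 says it "will be analyzed using CMH model adjusting for treatment group and stratification factors", then gives the decision rule: "Non-inferiority will be declared if the upper bound of the two-sided 95% CI of the hazard ratio is less than 1.3". The same section says that "the secondary endpoints below will be tested using a fixed sequence testing procedure". It gives the purpose as error control: "in order to maintain the overall two-sided Type I error rate at 0.05". When a test passes, "the claim of superiority (or noninferiority) will be considered met and the test will progress to the next comparison in sequence".

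The next bullet takes the same blood-pressure thresholds as a time-to-event endpoint: "Time to an increase in blood pressure will be analyzed using the Cox Proportional Hazards model adjusting for treatment group and randomization stratification factors". That step is assigned superiority only. MAP follows, and then, in a paragraph without a bullet, time to first Hb response. The last of these is a Cox analysis that carries the same 1.3 rule.

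**SAP.** Section 1 says the SAP is based on Amendment 4. The hypertension proportion is absent from the secondary endpoints in 4.3 and from the testing sequence in Table 5. In its place is time to first exacerbation over Weeks 28 to 52, in the last row of Table 5, for superiority and for non-inferiority with margin 1.8. Section 11.2.1.6 analyses that endpoint with a Cox model and a non-inferiority margin of 1.3. The diastolic threshold is 110 mmHg in 4.3 and Table 5, and 100 mmHg in 11.2.1.6.

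**Rule on changes.** Protocol 8.4.5: "Any significant changes to the analyses described in this protocol will be highlighted in the SAP and the Clinical Study Report".

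**The concern.** A non-inferiority test needs a margin on the scale that the analysis estimates. CMH on a proportion gives a common odds ratio, a risk ratio or a test of association. A hazard ratio needs event times and a model for them. The protocol states no margin on a CMH scale. Its general criterion of p < 0.05 does not fill the gap, because the usual CMH p-value tests no association rather than inferiority by a stated amount.

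Under the protocol's sequence the step is a gate, so the measure put in place of the hazard ratio could decide whether time to BP increase and MAP are tested at all. In an open-label trial that choice should not be left until data are in hand.

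The SAP pairs the hypertension test with a model that does yield a hazard ratio, but it does not leave one rule in force. Two margins and two event definitions remain, and the replacement is not identified as a change.

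**Working it through.** **1. The plan's own figures.** The documents give no event rate, power or margin derivation for hypertension. The only power figures are for the two primary endpoints, and both reproduce with 300 per arm:
- US: Φ(0.45 / (1.25·√(2/300)) − 1.96) = 99.3%, where 0.45 = 0.75 − 0.30 and −0.30 g/dL is the SAP's assumed difference.
- Ex-US: Φ(0.15 / √(2·0.8·0.2/300) − 1.96) = 99.6%.

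Neither bears on this point.

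**2. The passages side by side.**

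| | Protocol 8.4.3.2 | SAP 4.3 and Table 5 | SAP 11.2.1.6 |
|---|---|---|---|
| Endpoint | Proportion, no window stated | Time to first event, Weeks 28–52 | Time to event, Weeks 28–52 |
| Method | CMH | Not given there | Cox |
| Non-inferiority margin | Hazard ratio 1.3 | 1.8 (Table 5) | 1.3 |
| Diastolic threshold | > 100 mmHg | ≥ 110 mmHg | 100 mmHg (both ≥ and > appear) |
| Place in sequence | Before time to BP increase and MAP | Last | – |

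Neither SAP margin is labelled a hazard ratio. That reading follows from the Cox model and from 11.2.1.6 setting superiority at 1.

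**3. What a limit of 1.3 tolerates on each scale.** The control risk p is assumed. The hazard-ratio line also assumes proportional hazards and equal follow-up.
- Odds ratio: odds = 1.3·p/(1−p), converted back to a risk.
- Hazard ratio: 1 − (1−p)^1.3.
- Risk ratio: 1.3·p.

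| Assumed control risk | Odds ratio | Hazard ratio | Risk ratio |
|---|---|---|---|
| 10% | 12.6% | 12.8% | 13.0% |
| 30% | 35.8% | 37.1% | 39.0% |
| 40% | 46.4% | 48.5% | 52.0% |

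In the other direction, hazard ratio 1.3 corresponds to a risk ratio of 0.371/0.30 = 1.24 at 30% and 0.485/0.40 = 1.21 at 40%. Over control risks of 10% to 50% the match is a risk ratio of 1.28 down to 1.19, or an odds ratio of 1.32 up to 1.46.

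**4. Whether the decision can change.** Take equal observed risk p in both arms and n per arm. The upper 95% bounds are:
- RR: exp(1.96·√(2(1−p)/(np)))
- OR: exp(1.96·√(2/(np(1−p))))
- HR: approximately exp(1.96·2/√(2np))

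| n per arm, risk | RR | OR | HR |
|---|---|---|---|
| 300, 30% | 1.28 pass | 1.42 fail | 1.34 fail |
| 600, 20% | 1.25 pass | 1.33 fail | 1.29 pass |

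The same data can pass or fail 1.3 depending on the measure.

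**5. What the SAP's two margins imply.** For a true hazard ratio of 1, two-sided 0.05 and 1:1 allocation, events = 4(z₀.₉₇₅ + z_power)² / (ln margin)².

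| Margin | 80% power | 90% power |
|---|---|---|
| 1.3 | 457 | 611 |
| 1.8 | 91 | 122 |

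The stricter margin needs about five times the events (457/91 = 5.0). With 600 subjects, 611 first events cannot occur. With 1200, they would be 611/1200 = 51% of subjects.

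**The case against.** The best case for the plan is that this is a misplaced sentence which the SAP has already overtaken. The next protocol bullet fits a Cox model to the same thresholds, so a hazard ratio for nearly the same event is available. The identical 1.3 sentence sits properly under the Cox analysis of time to first Hb response. The SAP tests hypertension by Cox, last in its sequence, where it holds up nothing else.

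Much of this stands. A reader might infer that the protocol's sequence contains a step for which no decision rule could be computed, or that the later secondary tests are in real jeopardy. The documents do not support either reading. The rule is attached to the wrong analysis rather than impossible to evaluate, and the gating effect arises only if the protocol's sequence is followed instead of the SAP's. Even within the protocol, the place of time to first Hb response is uncertain because its paragraph is not a bullet.

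Three things survive:
- Borrowing the next bullet's hazard ratio would rewrite the plan, since that model has its own step and is assigned superiority only.
- The proportion has no stated window and treatment duration varies between subjects, so a proportion and a hazard ratio are not interchangeable.
- The SAP text available does not flag the replacement, and its own test has conflicting margins and thresholds. The Clinical Study Report, which 8.4.5 also names, is not among the documents.

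**Conclusion.** The point holds as a mismatch within protocol 8.4.3.2 together with an unreconciled replacement in the SAP. As written, the protocol applies a hazard-ratio limit to an analysis that does not estimate one, at a step that gates others under its own sequence. The SAP's Cox test removes that mismatch but leaves the non-inferiority margin at 1.8 or 1.3 and the diastolic threshold at 110 or 100 mmHg.

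The size depends on assumed event rates, since the documents give none. At 30% control risk the three readings of 1.3 span 35.8% to 39.0%. At 40% they span 46.4% to 52.0%. At 10% the spread is only 0.4 points. The pass-or-fail examples use large-sample standard errors and equal observed risks. This is a secondary endpoint and neither primary analysis is affected. It should be corrected because a confirmatory test should have one endpoint definition, one measure and one margin.

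**What to change.** Delete the CMH test with its hazard-ratio rule from the protocol sequence, or mark it as superseded. Flag in the SAP that time to first exacerbation replaces it, as protocol 8.4.5 provides. Reconcile protocol 8.4.3.2 with SAP 4.3, Table 5 and 11.2.1.6 so that both documents carry one Cox endpoint definition (time window and blood-pressure thresholds), one hazard-ratio margin with its justification, and one position in the sequence.

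If the proportion is kept, state a justified margin on a named CMH measure. Do not carry 1.3 over unchanged to a risk ratio: that is looser than a hazard ratio of 1.3, tolerating 39.0% against 37.1% at an assumed 30% control risk and 52.0% against 48.5% at 40%.

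The edits are a few sentences and no new data are needed. The real work is justifying the margin, since none of the documents derives 1.3 or 1.8 for this endpoint.
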